#### 13.11.2. Handling of Missing Data

In order to identify each type of missing data, outcome scales will be coded for every patient and visit according to the following scheme (see also Bagiella, 2010):

- 1 = valid (complete task)
- 2 = unable to complete (stroke-related neurological reason) [describe reason]
- 3 = not completed (different reasons, not stroke related) [describe reason]

#### 13.11.3. Worst Rank Imputation

For outcome scales with code "2" a worst rank imputation will be introduced for the corresponding patients since these data are informatively missing (missing not at random, MNAR). These missing data are replaced by the worst possible score of the corresponding outcome scale.

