#### 4.1.1. **Primary Variables**

The following psychometric tests are combined by multivariate analysis with their score changes from baseline at 180 and 360 days after baseline (7 and 13 months after the onset of ischeamic stroke):

- Stroop Color Word test (Stroop)
- Trail-Making-Test Part A (TMT-A)
- Digit Span Backwards Task (DS-BW)
- Digit Symbol (DS-WPSI)

- Verbal Fluency Test CFL Version (VFT-CFL)
- Rey Auditory Verbal Learning Test (RAVLT)

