#### 13.7. Multiplicity

Multiplicity regarding multiple primary outcome measures is controlled by the chosen correlation-sensitive, multivariate test procedure (Wei-Lachin procedure, see also section 13.9).

Mutiplicity regarding the two primary points in time is controlled by means of the principle of *a priori* ordered hypotheses (fixed sequence approach). The procedure of *a priori* ordered hypothesis is most powerful with full control of alpha (for control of alpha using stepwise testing see Maurer W, Hothorn LA, Lehmacher W 1995). The sequence and nature of the a priori ordered test-statistical hypotheses of the trial is defined as follows:

- 1. Combined cognitive outcome measures as defined in section 13.3.2, score changes from baseline to day 180 (month 4 post stroke), multivariate analysis, generalized Wilcoxon-Mann-Whitney test (Wei-Lachin procedure)
- 2. Combined cognitive outcome measures as defined in section 13.3.2, score changes from baseline to day 360 (month 13 post stroke), multivariate analysis, generalized Wilcoxon-Mann-Whitney test (Wei-Lachin procedure)

The principle of *a priori* ordered hypotheses is embedded in the well-known general principle of closed testing. The pre-planned chain of hypotheses can be tested in a confirmatory way with the same full alpha value; each test result smaller than alpha will be statistically significant as long as the preceding test result was also significant.

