#### 13.11. Accounting for missing data

#### 13.11.1. Missing Data Problems – General Considerations

Missing data are a problem in every data analysis. Of course, there are always missing data of the type 'missing completely at random' (MCAR), which in principle will not bias the results; the analysis procedure should be able to cope with partially missing data of such a type. In many studies this type of data is treated by LOCF replacement (Last Observation Carried Forward) as far as there exist follow-up measurements at previous visits.

In a study like the one planned there might also be informatively missing data (missing not at random, MNAR): participants of the study died or are unable to complete the tests because of brain-related impairment. Neglecting these missing data might introduce bias.

A reasonable policy for minimizing bias in the case of informatively missing data (MNAR) is the replacement of these missing data by assigning the worst possible score, or a score worse than those observed. It should be noted that this strategy is only reasonable if rank-based robust procedures are used for the data analysis.

The worst rank imputation procedure was recommended by Lachin in his seminal paper about the missing data problem for data missing because of mortality when performing an exercise test (Lachin, 1999). This procedure was also used when analyzing non-fatal outcomes in studies where mortality was a problem (Lusben, 2002; McMahon, 2001). Recently a similar procedure has been proposed by the 'Traumatic Brain Injury (TBI) Clinical Trials Network' when designing the COBRIT study (Bagiella, 2010).

Temkin (2007) included deaths with the worst rank for the significance tests of neuropsychological scales but excluded deaths for the calculation of descriptive statistics (e.g., mean, SE estimates). Thus, significance tests reflect all patients with estimation of missing data while the descriptive statistics reflect only the actually observed assessments. We prefer not excluding deaths from descriptive statistics, since the study treatment with more deaths would artificially have better neuropsychological scores while a study treatment preventing deaths would be burdened by rather severe scores of survived patients. The use of robust descriptive statistics in this study allows the inclusion of worst rank scores for deaths also in

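### Worst-rank imputation is written for the raw score, but both confirmatory tests rank change from baseline, so an imputed case near the floor is not ranked worst

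*Protocol*

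**What the plan says.** Protocol 4.1.1 defines the primary variables as six cognitive tests "combined by multivariate analysis with their score changes from baseline at 180 and 360 days after baseline". Section 13.7 repeats this in both ordered hypotheses; the second reads "score changes from baseline to day 360 (month 13 post stroke), multivariate analysis, generalized Wilcoxon-Mann-Whitney test", and the first is the same for day 180.

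Section 13.11.1 is concerned with informatively missing data: "participants of the study died or are unable to complete the tests because of brain-related impairment". Its policy is "replacement of these missing data by assigning the worst possible score, or a score worse than those observed", and it cites worst-rank methods in support. Under 13.11.2, "outcome scales will be coded for every patient and visit", with code 2 for a stroke-related neurological inability to complete. The operative rule for code 2 is in 13.11.3, under a heading that speaks of worst rank: "These missing data are replaced by the worst possible score of the corresponding outcome scale". The companion rule for code 3 in 13.11.4 also works on the raw scale. Nowhere does the protocol say that the worst rank is given to the change.

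**The concern.** A worst-rank method is meant to place every informatively missing patient below every tested patient. Inserting the worst raw score achieves that if the raw follow-up score is what gets ranked. Here baseline is subtracted first, so the penalty is as large as the patient's distance from the floor at entry. Patients with good baselines are penalised heavily, and patients already near the floor hardly at all.

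Section 13.9 itself says that floor and ceiling effects are known from many cognitive scales, so baselines near the floor cannot be dismissed. The six scales will differ in how close their baselines lie to the worst score, so the same event carries a different penalty on each component of the combined statistic.

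There is a second consequence. Codes are assigned at every visit and 13.11.3 exempts none. Read literally, a scale coded 2 at baseline also receives the worst score. Untestable at both visits then gives a change of 0, and untestable at baseline with any later result gives a gain measured from the bottom of the scale.

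**Working it through.** No figure in the protocol bears on this point, and the sample size of 145 per group is unaffected. The check is algebra, followed by two simulations on assumed distributions.

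**Algebra.** Let W be the worst score, B the baseline and F the observed follow-up. A tested patient contributes F − B and an imputed patient W − B. With W = 0 and higher scores better:

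- Untestable patient with B = 3: change = 0 − 3 = −3.
- Tested patient falling from 40 to 30: change = 30 − 40 = −10.
- The untestable patient ranks better than the tested one.
- With B = 0, the imputed change is 0, the same as a patient who did not change.

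On a timed test, where higher is worse, the same happens to patients with slow baseline times.

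**Rank position on a bounded scale.** All inputs are assumptions: scores rounded to 0–15, mean gain 0.5 in tested patients, and four settings of mean, SD and baseline to follow-up correlation. In the setting 5, 3, 0.6, the mid-percentile of (0 − B) among observed changes is about the 43rd for B = 0, the 29th for B = 1 and the 17th for B = 2. Averaged over imputed patients:

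| Mean, SD, correlation | Mean / SD | Missingness unrelated to baseline | Missingness weighted to poor baselines |
|---|---|---|---|
| 5, 3, 0.6 | 1.7 | 7.8 | 18.7 |
| 4, 2.5, 0.6 | 1.6 | 8.2 | 19.0 |
| 6, 2.5, 0.7 | 2.4 | 2.1 | 8.5 |
| 7.5, 2.5, 0.7 | 3.0 | 0.6 | 3.9 |

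Entries are average percentiles; a true worst rank is 0. The weighting lets the chance of missingness fall by a factor of e for each SD of better baseline. Patients at B = 0 make up 6.6%, 8.0% and 1.4% of the first three settings, so the 43rd-percentile case is the extreme one.

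**Loss of signal on one scale.** Assume normal baselines, correlation 0.7, mean improvement 0.3 SD, no treatment effect among tested patients, and untestable proportions p1 and p2 in the two arms. A true worst rank gives MW = 0.5 + (p2 − p1)/2, so 5% against 15% gives 0.5 + 0.10/2 = 0.55. The simulated worst-rank values run from 0.5486 to 0.5498, which agrees. Under the rule as written, with 5% against 15%:

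- Mean baseline 1.5 SD from the floor, untestable patients 1 SD worse at entry: MW 0.5317 against 0.5486. Share kept = 0.0317 / 0.0486 = 65%.
- Mean baseline 1.5 SD from the floor, baselines alike: 0.5433 against 0.5495. Share kept = 0.0433 / 0.0495 = 87%.
- Mean baseline 3 SD from the floor: 94% kept (1 SD worse at entry) and 99% kept (baselines alike).

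At 2 SD the corresponding figures are 77% and 94%.

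**The case against.** Five points can fairly be made against the concern.

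First, the size rests on invented baselines. The protocol gives none, and 6.5 removes some floor patients (MMSE below 12, major communication deficit, marked aphasia). This stands: the effect is small on scales far from the floor. But none of those criteria screens on the six tests themselves.

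Second, a reader might infer that deaths are misranked in both confirmatory tests. The documents do not support that. The codes in 13.11.2 have no category for death, so 13.11.3 reaches deaths only if they are coded 2 or through 13.11.1. The full analysis set in 13.12.3 requires at least one post-baseline observation of a primary criterion. On a plain reading, a patient who dies before day 180 enters neither test.

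Third, a reader might assume that patients with the poorest baseline cognition are the most likely to become untestable or die. That is plausible, but the protocol offers no evidence for it, so the right-hand column of the table is a scenario and not an expectation.

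Fourth, the rule is identical in both arms and uses a baseline measured before treatment. No inflation of type I error follows, and none is claimed.

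Fifth, the SAP could assign the rank to the change, and the heading of 13.11.3 points that way. But the protocol does not leave the matter open: it fixes a raw score in 13.11.3 and a change variable in 13.7. An SAP that follows both reproduces the problem. The missing cap for timed tests is different; that is ordinary SAP detail.

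**Conclusion.** The point holds in a limited form. The stated rule misses its own stated purpose: the rank of an imputed case depends on baseline, and near the floor it is not the worst rank.

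Under the assumed distributions, the average imputed case sits at about the 1st to 8th percentile of observed changes, or about the 4th to 19th if missingness is concentrated at poor baselines. Imputed cases still rank low on average. What is lost is part of the penalty, by an amount that differs between scales, and it matters only when informative missingness differs between arms. The dilution pulls towards equality whichever arm has more untestable patients, so it can hide a harm as well as a benefit. The conclusion that the rule and the analysed variable do not fit together needs no assumption; every figure for its size does.

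**What to change.** Amend 13.11.3 so that a follow-up value with code 2 receives a change worse than every observed change on that scale, all such cases tied, whatever the baseline. Say that the same applies to a death where the patient is in the full analysis set and the worst rank of 13.11.1 is meant to apply.

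State also that the worst-score replacement applies to follow-up visits only and never to a baseline used to compute change. For a scale untestable at baseline but completed later, no change can be computed, and the SAP should say how it is handled. Ranking those patients on their follow-up score is not an option, because follow-up and change values cannot share one Mann-Whitney ranking. Setting the scale to missing would treat a neurologically caused gap as random, and that should be acknowledged.

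The cap for timed tests can be left to the SAP. The cost is a few sentences in the protocol and SAP and a few lines of code, settled before unblinding. The sample size does not change.

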#### 4.2.1. Secondary Variables

- Score and score changes from baseline of the individual primary outcome scales at 180 and 360 days after baseline (7 and 13 months after the onset of ischeamic stroke)
- Score and score changes from baseline NIH Stroke Scale at 180 and 360 days after baseline
- Score and score changes from baseline Modified Rankin Score at 180 and 360 days after baseline
- Score and score changes from baseline Hospital Anxiety and Depression Scale at 180 and 360 days after baseline
- Score and score changes from baseline EQ-5D-5L at 180 and 360 days after baseline
- Safety parameters including Adverse Events at 180 and 360 days after baseline

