#### 9.2.3. Modified Rankin Score

The Modified Rankin Scale (Van Swieten et al, 1988) is a functional outcome scale measuring global outcome. It is used for grading the outcome and the level of disability after a stroke. The Modified Rankin Scale is a 7-point ordinal scale with a score of 0 indicative of no residual symptoms at all and the worst possible score of 6 which is assigned in case of death. The Modified Rankin Scale is observer rated and takes about 5 min to complete.

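### The worst-rank rule in 13.11.3 fills in the worst raw score, but the confirmatory tests rank changes from baseline, so code 2 patients do not reliably receive the worst rank

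*Protocol*

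**What the plan says.** **What is ranked.** Section 4.1.1 defines the primary variables as six tests "combined by multivariate analysis with their score changes from baseline at 180 and 360 days after baseline". Section 13.7 repeats this in both ordered hypotheses: "score changes from baseline to day 180" first, then "score changes from baseline to day 360".

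**What is imputed.** Section 13.11.2 codes each scale at each visit. Code 2 means unable to complete for a stroke-related neurological reason. For code 2, section 13.11.3, headed Worst Rank Imputation, says: "These missing data are replaced by the worst possible score of the corresponding outcome scale".

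**The stated purpose.** Section 13.11.1 presents the approach as protection against bias from death and brain-related inability to be tested. In general terms it offers "assigning the worst possible score, or a score worse than those observed". Section 13.11.3 adopts only the first of these two options.

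**Secondary scales.** Section 4.2.1 lists "Score and score changes from baseline Modified Rankin Score at 180 and 360 days after baseline", and 9.2.3 describes "the worst possible score of 6 which is assigned in case of death". Section 13.5 lists the mRS as a follow-up score and the NIHSS as a change.

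**The concern.** The worst raw score gives the worst rank only if follow-up scores themselves are ranked. Once changes are ranked, the imputed value depends on how good the patient was at baseline. A patient who started near the floor has little left to lose and receives a small negative change, although the outcome is among the worst in the trial.

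Nothing in the protocol reconciles the two rules. The rule for code 3 in 13.11.4 also transforms back to the raw scale, which fits an order of imputing first and forming the change afterwards. A programmer following 13.11.3 literally would therefore not produce worst ranks.

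Low baselines are plausible here: 13.9 acknowledges floor effects in many cognitive scales, and 6.5 excludes on the MMSE only below 12. At stake is the sensitivity of the primary statistic to benefit or harm that acts through neurological inability to be tested.

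**Working it through.** **Step 1. Direct subtraction.** On a scale with worst score 0, a code 2 patient with baseline b gets an imputed change of 0 − b = −b. A survivor who declines by D ranks worse only if D > b. On an illustrative 15-word recall:

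- code 2 patient, baseline 3: 0 − 3 = −3
- survivor from 10 to 6: 6 − 10 = −4, ranked worse than the code 2 patient
- survivor from 10 to 8: 8 − 10 = −2, ranked better than the code 2 patient

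The misranking is therefore real but conditional on the size of the decline.

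**Step 2. The plan's own figure.** The protocol gives no figure for the effect of this rule. Its related figure, 145 per group (13.8), can be approached with d = 0.35, the π/3 factor for the rank test and six scales with correlation 0.6:

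- 2 × (1.960 + 1.282)² / 0.35² = 171.5
- 171.5 × π/3 = 179.6
- 179.6 × (1 + 5 × 0.6)/6 = 119.8, so 120
- 120/0.85 = 141.2, so 142, within 3% of 145

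The imputation rule does not enter this calculation, so the sample size is unaffected.

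**Step 3. The signal under true worst rank.** Assume event rates of 10% on placebo and 5% on active and no effect in survivors. These rates are not in the protocol. Then

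MW = 0.95 × 0.90 × 0.5 + 0.95 × 0.10 × 1 + 0.05 × 0.10 × 0.5 + 0.05 × 0.90 × 0 = 0.4275 + 0.0950 + 0.0025 + 0 = 0.525.

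**Step 4. The signal under the written rule.** Let q be the average share of survivors outranked by an event patient. The second term becomes 0.095(1 − q) and the last 0.045q, so

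MW = 0.525 − 0.05q, and the share of the 0.025 signal that is kept is 1 − 2q.

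**Step 5. The size of q.** Simulation of 400,000 baseline and follow-up pairs per setting, under these assumptions: normal scores, values below the floor set to the floor, correlation 0.6 or 0.8, mean survivor change 0 or +0.3 SD, and event patients drawn either at random or with baselines 0.5 SD lower.

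| Floor below baseline mean | q, all event patients | MW | Signal kept |
|---|---|---|---|
| 1.5 to 2 SD | 2% to 19% | 0.516 to 0.524 | 62% to 96% |
| 2.5 to 3 SD | 0.2% to 6% | 0.522 to 0.525 | 87% to nearly 100% |

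The ends of the first row follow from step 4: 1 − 2 × 0.02 = 0.96 and 1 − 2 × 0.19 = 0.62. In the second row the largest q is 0.063 before rounding, and 1 − 2 × 0.063 = 0.874. For event patients from the lowest baseline quarter, with the floor at 1.5 to 2 SD, q is 8% to 37%. Under true worst rank it is 0% in every setting.

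**Step 6. A second model.** Take a normal baseline truncated at 0 with coefficient of variation 0.3 to 0.8, correlation 0.5 to 0.7, and code 2 patients from the lower baseline half at 5% versus 10%. True worst rank gives MW 0.528 to 0.531 and the written rule 0.520 to 0.530. The direction and order of size agree with step 5.

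**Step 7. Scale against the precision of the test.** With 145 per group, the null standard error of MW on one scale is √(291/(12 × 145 × 145)) = 0.0340. For the six-scale average with correlation 0.6 it is 0.0340 × √(4/6) = 0.0277. The largest loss in step 5, 0.05 × 0.19 = 0.0095, is about a third of that, and this assumes the same event rates and loss on all six scales.

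**The case against.** The strongest case on the other side is that the defect is small and the alarming readings go too far. Much of that stands.

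- **Validity.** A reader might infer that the primary test is biased. It is not. Baselines are randomised, so favouring patients with poor baselines favours neither arm, and the test holds its level under the null. The cost is attenuation.
- **Breadth.** A reader might infer that code 2 patients outrank every survivor who declined. Step 1 shows they do not.
- **Deaths.** A reader might take the rule as settled for all deaths. The codes in 13.11.2 have no category for death, and a death unrelated to the stroke would literally fall under code 3. The FAS definition in 13.12.3 also requires a post-baseline observation. Section 13.11.1 shows the intention to give deaths worst-rank scores, so deaths belong here only where they are handled under this rule. The point is firmest for untestable patients.
- **Size.** The 8% to 37% range concerns the lowest baseline quarter only. Over all event patients the range is 2% to 19%, and the exclusions in 6.5 (MMSE below 12, NIHSS item 9 of 2 or more, dementia from the index stroke) remove some baselines near the floor.
- **mRS.** Baseline 5 then death is +1, while a survivor from 1 to 3 is +2, so the change score shows the same feature. But 13.5 lists the follow-up mRS, on which death at 6 is the true worst rank, and this analysis is exploratory. It says nothing about the primary test.
- **TMT-A.** The absence of a stated worst completion time is scoring detail that may be left to the SAP and is not a defect in itself.

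None of this reconciles 13.11.3 with 13.7.

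**Conclusion.** The point holds in limited form. The protocol fixes both the ranked variable (change) and the imputed value (worst raw score), and together they do not deliver the worst rank that 13.11.3 promises. The null is protected; an effect acting through neurological inability to be tested is diluted. If baselines lie 1.5 to 2 SD above the floor, 62% to 96% of such a signal survives; at 2.5 to 3 SD, 87% to nearly all of it. These figures rest on assumed normal scores, correlations, floor positions and event rates that the protocol does not give. The contradiction itself rests on no assumption. The sample size is not affected. The correction should be made before unblinding; the finding does not call the design into question.

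**What to change.** Reword 13.11.3 so that, for each of the six primary scales oriented with higher as better, a patient who has an observed baseline and falls under the worst-rank rule at the analysed visit receives one common value below the lowest observed change in either arm, with all such patients tied at the bottom.

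Confine the sentence to patients with an observed baseline. Codes apply at every visit, and a patient untestable at both baseline and follow-up would otherwise move from a change of 0 to the bottom rank without that having been decided.

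Apply the same wording where NIHSS or mRS changes are ranked. The follow-up mRS score listed in 13.5 needs no change. With a common bottom value, no worst completion time has to be chosen for TMT-A for these patients.

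Cost: one sentence and one programming step. No new data and no more patients are needed.

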#### 13.11.4. LPCF Imputation

For outcome scales with code "3" a LPCF replacement will be introduced (Last Percentile Carried Forward) as far as previous follow-up evaluations exist. This method carries forward the actual status information of the patient population, using the percentile value with back transformation to raw scale, instead of last value carried forward. This approach was recently developed and recommended by O'Brien, Zhang and Bailey (2005) for the analysis of data from chronic, progressive diseases as dementia. According to their simulation study the calculated estimators should be negligibly biased by missing data. If no general change of patients over time occurs the method is more or less identical with LOCF (Last Value Carried Forward), if change occurs bias is minimized.

If no previous follow-up measurement exists, the outcome scale remains missing. It is important to note that the chosen multivariate test procedure (Wei-Lachin procedure) can handle partially missing single scales of type MCAR (missing completely at random).

